6.5. Monitoring plan

As the sponsor of this clinical investigation, Masimo Corporation is required by 21 CFR Part 812, of the Food and Drug Administration regulations to monitor and oversee the progress of the investigation. The monitor(s) assigned by Masimo Corporation to this task will be trained on departmental SOPs on conduct and monitoring of sponsored studies.

In accordance with good clinical practices guidelines, there will be at least three scheduled monitoring visits to ensure overall regulatory compliance of the study:

- An initiation visit, prior to any subject enrollment to confirm site readiness, and to document training on the study protocol and procedures, and use of equipment.
- At least one monitoring visit during initial enrollment, and/or every 2-4 weeks until completion of the study.
- A final close out visit after the last patient had finished the study.

The monitor will contact and visit the investigator and will be allowed, on request, to have access to all source documents needed to verify the entries in the CRFs and other GCP-related documents (IRB approvals, IRB correspondences, and ICFs) provided that subject confidentiality is maintained in agreement with HIPAA regulations.

It will be the monitor's responsibility to inspect the CRFs at regular intervals throughout the study, to verify the adherence to the CIP and the completeness, consistency and accuracy of the data being entered on them.

During each visit, the monitor will also verify presence of informed consent, adherence to the inclusion/exclusion criteria, and documentation of SAEs/SADEs and protocol deviations/violations, and check CRF against source documentation.

After each visit, the monitor will provide a monitoring letter to the investigator within 4 weeks of visit completion. The monitoring letter will detail findings and open action items observed during the visit. It is the responsibility of the Principal Investigator and Study Coordinator(s) to respond to the findings of the monitoring letter, and complete any open action items as soon as possible but no later than 60 days of receiving the monitoring letter. Any open action items not completed within the time allowed may be sufficient grounds for study site suspension or termination; it will be up to the sponsor to determine whether any incomplete action items are sufficient grounds for suspension or termination. Depending on the quality of the data and/or changes to factors affecting patient safety, additional monitoring visits may be necessary according at the sponsor's discretion.

7. STATISTICAL DESIGN AND ANALYSIS

7.1. Acceptance Criteria

For validation studies, acceptance criteria are determined by Masimo specifications.

7.2. Sample Size

Analysis methods consistent with Receiver Operating Characteristics (ROC) curves will be used. Therefore, the sample size was determined to meet simultaneous requirements for both Sensitivity and Specificity. The PASS 2019 software package was used to calculate the appropriate sample size using the Confidence Intervals for One-Sample Sensitivity and Specificity module. [REDACTED]

[REDACTED]

[REDACTED]

[REDACTED]

[REDACTED]

7.3. Statistical Analysis**7.3.1. Exclusion**

The following subjects will be excluded from data analysis:

- Subjects where the paired reference or test ECG did not provide readable ECG waveforms as determined by medical personnel.
- Subjects who presented as having Afib at the time of enrollment, but who provided ECG waveforms with characteristics inconsistent with an Afib diagnosis (as determined by medical personnel).

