6. DESIGN OF THE CLINICAL INVESTIGATION

6.1. General

This is a prospective, nonrandomized, single arm study. The study endpoints are designed to validate the performance of Masimo INVSENSOR00057 in detecting Afib. The validation of the Afib detection function in the investigational device may be determined using data collected from this study, in addition to data from other Masimo sponsored studies.

The primary endpoint of this study will be the analysis of sensitivity and specificity of Masimo INVSENSOR00057 Afib detection function when compared to data collected using an FDA-cleared ECG monitor.

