6.4.3. Data Collection Procedure

6.4.3.1. The subject will be seated and/or lying-in supine position and should refrain from excessive movement during the study. Subject medical history and demographic information including age, sex, skin pigmentation, ethnicity, height, and weight may be recorded for data analysis and/or subject safety monitoring purposes.

6.4.3.3. INVSENSOR00057 will be placed on the subject's wrist according to the Investigator's Brochure. [REDACTED]

[REDACTED] The device may be repositioned, as needed, to ensure proper placement.

The site of device placement should be assessed throughout the duration of the study. If there are any signs of loss of skin integrity and/or loss of circulation or perfusion, the device should be repositioned. In the unlikely event of emergency

defibrillation, the device must be removed prior to defibrillation.

6.4.3.4. [REDACTED]

6.4.3.5. Upon successful placement and Bluetooth pairing of the device, data collection will be initiated [REDACTED]
[REDACTED]
[REDACTED]

6.4.3.6. The subject will be requested to take manual ECG measurements on the INVSENSOR00057 [REDACTED]
[REDACTED]
[REDACTED]

6.4.3.7. Observations may be recorded on the case report form (e.g., subject position, timing and duration of manual measurements on the INVSENSOR00057 device).

6.4.3.8. At the conclusion of the procedure, the electrodes and device will be removed.

[REDACTED]
[REDACTED]

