7.3.2. Afib Classification Accuracy Calculations

Classification accuracy will be measured by Sensitivity and Specificity as defined below.

Test \ Reference	AFIB	No AFIB
AFIB	TP	FP
No AFIB	FN	TN

$$Sensitivity = \frac{TP}{TP + FN}$$

$$FalseAlarmRate = 1 - Specificity = \frac{FP}{FP + TN} = \frac{FP}{TotalNegativeEvents}$$

$$PPV = \frac{FP}{TP + FP} = \frac{FP}{TotalPositiveDetections}$$

$$Accuracy = \frac{TP + TN}{TP + FP + FN + TN}$$

Analysis methods consistent with Receiver Operating Characteristics (ROC) curves will be used.

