8.3. Case Report Forms

The site shall capture study data in case report forms (CRFs) for each subject enrolled, to be provided to the sponsor. CRFs may be in paper or electronic format through electronic data capture (EDC) software. Masimo shall ensure that systems used for electronic CRFs are compliant with the requirements of 21 CFR Part 11 and ISO / IEC 27001 Certification. The CRFs will be completed and signed by the principal investigator or delegate. This also applies to those subjects who fail to complete the study. If a subject withdraws from the study, the reason must be noted on the CRF. Case report forms are to be completed on an ongoing basis. CRF entries and corrections will only be performed by study site staff, authorized by the investigator. For paper CRFs, entries and corrections to the CRF will be made following Good Documentation Practices.

The CRF may include the following information, including but not limited to: inclusion / exclusion criteria, whether subject consent was obtained before start of study, demographic information, device readings, and if occurrence of any adverse event, protocol deviation, and device deficiencies, etc. The CRFs will be signed by the PI or delegate to attest that the data are complete and accurate.

CRF entries will be checked by the study monitor and any errors or inconsistencies will be queried to the site on an ongoing basis. Any changes made within an electronic CRF will be tracked by audit trail. Any changes on a paper CRF will be made directly on the CRF and will be initialed and dated by the person making the change. Query resolution will be assessed and confirmed by study monitor during site visit.

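### Section 7.3.1 drops subjects whose device ECG alone is unreadable, so the planned sensitivity is conditional on a readable device trace, and no visible text labels it so or reports the unreadable share

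*Combined protocol and SAP*

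**What the plan says.** Section 7.3.1 lists two groups to be left out of data analysis. The first is "Subjects where the paired reference or test ECG did not provide readable ECG waveforms as determined by medical personnel". The second is "Subjects who presented as having Afib at the time of enrollment, but who provided ECG waveforms with characteristics inconsistent with an Afib diagnosis", again as judged by medical personnel; this bullet does not say whether the reference or the device waveform is meant. Neither exclusion is confined to one analysis, and no second analysis is described.

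Section 7.3.2 cross-classifies a device result of AFIB or No AFIB against the same two reference categories and defines sensitivity as TP/(TP + FN). There is no category for an unreadable trace or for no result.

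Section 6.1 states the target without a readability qualifier: "The primary endpoint of this study will be the analysis of sensitivity and specificity of Masimo INVSENSOR00057 Afib detection function". Section 6.3 admits only subjects with confirmed active AF. Section 7.1 says "For validation studies, acceptance criteria are determined by Masimo specifications" and does not name the denominator to which those specifications refer.

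On data collection, 6.4.3 says "The subject will be requested to take manual ECG measurements on the INVSENSOR00057", in the plural; the text that follows is redacted. It also says "The device may be repositioned, as needed, to ensure proper placement". Section 8.3 introduces the contents of the case report form, device readings among them, with "The CRF may include the following information, including but not limited to".

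**The concern.** The first bullet treats two different failures alike. If the reference is unreadable, the true rhythm is unknown and the subject cannot be classified, so exclusion is legitimate. If only the device trace is unreadable, the truth is known and the failure belongs to the device under test. Removing that subject makes the result depend on the device's own performance.

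Because 6.3 enrols only subjects in AF, nearly everyone lost this way would otherwise count towards sensitivity. Under 7.3.2 such a subject is neither a true positive nor a false negative and leaves the denominator. The reported sensitivity then stays the same whether 1% or 10% of device traces were unreadable.

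A reader could not repair this afterwards, because the visible text plans neither the unreadable proportion nor an all-subject figure. Nor does it fix in advance which denominator faces the acceptance criterion.

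**Working it through.** **Plan figure.** The plan gives no sensitivity, unreadable rate or visible acceptance limit. The planned size of about 100 (synopsis) cannot be reproduced because the inputs in 7.2 are redacted. That is not a fault of the plan, and this point does not depend on it.

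**Notation.** All three quantities are assumptions. Among subjects with a readable AF reference, u is the proportion with an unreadable device trace, s is the detection rate in readable device traces, and d is the detection rate in unreadable ones, with no result counted as not detected. Each subject has one device result.

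**Formulas.**
- Planned estimate: s
- All-subject sensitivity: s(1 − u) + du
- Planned minus all-subject: s − s(1 − u) − du = u(s − d)

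The difference is positive if d < s, zero if u = 0 or d = s, and negative if d > s.

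**Numbers at s = 95%.** The plan would report 95% in every row.

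| u | all-subject, d = 0 | all-subject, d = 100% | planned minus all-subject |
|---|---|---|---|
| 1% | 94.05% | 95.05% | +0.95 to −0.05 points |
| 2% | 93.1% | 95.1% | +1.9 to −0.1 |
| 5% | 90.25% | 95.25% | +4.75 to −0.25 |
| 10% | 85.5% | 95.5% | +9.5 to −0.5 |

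At u = 10% and d = 50%, the all-subject figure is 0.95 × 0.90 + 0.50 × 0.10 = 90.5%, a difference of 4.5 points.

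**Whole-number illustration** (exact Clopper-Pearson 95% intervals). Assume 100 subjects with a readable AF reference, 10 unreadable device traces, and 86 of the other 90 detected.
- As planned: 86/90 = 95.6% (89.0 to 98.8)
- All subjects, none of the 10 detected: 86/100 = 86.0% (77.6 to 92.1)
- All subjects, 5 of the 10 detected: 91/100 = 91.0% (83.6 to 95.8)
- All subjects, all 10 detected: 96/100 = 96.0% (90.1 to 98.9)

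**When the gap exceeds sampling error.** Take 100 AF-reference subjects and about 95% detection in readable traces, rounded to whole subjects. The test is whether the all-subject figure falls below the lower limit of the planned interval.
- d = 0, 7 unreadable: 88/93, lower limit 87.9, against 88.0%. Not below.
- d = 0, 8 unreadable: 87/92, lower limit 87.8, against 87.0%. Below.
- d = 50%, 15 unreadable: 81/85, lower limit 88.4, against (81 + 7.5)/100 = 88.5%. Not below.
- d = 50%, 16 unreadable: 80/84, lower limit 88.3, against (80 + 8)/100 = 88.0%. Below.

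**Where the unreadable share might have been planned.** The screening log in 6.4.2 covers eligibility failures. Section 7.4 covers dropout and does not mention unreadable traces. Section 14.4 has individual device deficiencies recorded but plans no rate. None of these commits to reporting the share.

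**The case against.** The strongest reply is that readable-only sensitivity is a legitimate target. The endpoint concerns the detection function, 7.3.2 speaks of classification accuracy, and performance on interpretable traces fits both. This stands, provided the estimate is labelled as conditional and shown with the unreadable share. The visible plan does neither.

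The unreadable share may also be close to zero. Subjects sit or lie still, the device may be moved to a better position, and more than one manual measurement is requested. The exclusion is by subject, so it may apply only when no readable pair was obtained, and the redacted steps may contain a repeat rule. All of this bears on size and stands: no value of u, 10% included, has support in the documents. It also means that one device result per subject cannot be taken for granted, so the fix must say how that result is defined.

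The count will presumably exist, since 7.3.1 cannot be applied without judging readability. That is fair: the clear gap is in reporting. The permissive wording of 8.3 is weak evidence that the data would not be collected.

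Specificity is also part of the primary endpoint. That matters little here, because 6.3 and the second bullet of 7.3.1 leave essentially only AF subjects in this study. It would matter for reference-negative recordings in the pooled data that 6.1 allows.

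A reader might infer that the second bullet also removes subjects on the device trace. The text does not say so; it is ambiguous and needs clarifying, no more.

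**Conclusion.** The point holds as one of analysis set and reporting, and should be fixed. It is certain from 7.3.1 and 7.3.2 that an unreadable device trace alone removes a subject with a known AF reference and that the resulting sensitivity is conditional on readability. No visible text says so, reports the proportion or gives the all-subject figure; the redacted parts of 6.4.3 and 7.2 could hold a repeat rule or an allowance.

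The size is unknown. At an assumed s of 95% it is about 1 point or less at u = 1%, and between 9.5 points too high (d = 0) and 0.5 too low (d = 100%) at u = 10%.

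A reader might infer that the trial will overstate sensitivity, or by how much. The documents support neither. An upward shift is plausible because it needs only d < s, but nothing visible says how the device behaves on poor traces or how often they occur.

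**What to change.** - In 7.3.1, limit the first exclusion to subjects with an unreadable reference ECG, and state that the second bullet is judged on the reference waveform.
- For all subjects with a readable AF reference, report sensitivity from the AFIB or No AFIB result the device issued. Count a subject as not detected only when no result was issued.
- Beside it, report sensitivity in readable device traces, labelled as conditional. Give 95% confidence intervals for both figures and the number and proportion of unreadable and of no-result device ECGs.
- Where a subject has several manual measurements, use the protocol's own measurement and repeat rule to define the single per-subject result, fixed before data are seen.
- If reference-negative recordings enter this analysis or pooled data, report their no-result count in the same way.
- State in advance which sensitivity figure the criterion in 7.1 applies to.
- Require the device result and trace readability to be recorded for every subject.

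The cost is two edited bullets, one added results row and two required data fields. The sponsor should also check that the sensitivity assumed in 7.2 and the criterion in 7.1 use the chosen denominator. The downside is that the sensitivity figure may be less favourable.

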6.3. Subjects

Inclusion Criteria

- Subject is 18 years of age or older.
- Subject is confirmed to have active atrial fibrillation at the time of enrollment.

Exclusion Criteria

- Subject is confirmed to have concurrent active arrhythmias (e.g., PVCs, bradycardia, etc.) at the time of enrollment.
- Subject is allergic to adhesives or ECG gel.
- Subject whose skin is not intact in or at the vicinity of the device placement site.

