6.4. Procedures

6.4.1. Recruitment and Pre-Screening

Subjects will be recruited from local clinics or cardiology offices. Subjects who present with active atrial fibrillation during their regular doctor visit will be recruited for the study.

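### The AF-inconsistency exclusion in 7.3.1 does not say which ECG decides or, in readable text, that the reader is masked: one reading can drop device misses, the other can empty the specificity denominator

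*Combined protocol and SAP*

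**What the plan says.** Section 7.3.1 has two exclusions, both applied to whole subjects and both decided by medical personnel. The first concerns readability and names both tracings, the "paired reference or test ECG". The second removes "Subjects who presented as having Afib at the time of enrollment, but who provided ECG waveforms with characteristics inconsistent with an Afib diagnosis" and does not say which tracing is meant. Neither bullet mentions masking, reading order or the number of readers.

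Section 6.1 describes the design: "This is a prospective, nonrandomized, single arm study". It makes the FDA-cleared monitor the comparator and defines the endpoint: "The primary endpoint of this study will be the analysis of sensitivity and specificity". Section 7.2 sizes the study on both measures together; its inputs are redacted.

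Entry is confined to AF. Section 6.3 requires: "Subject is confirmed to have active atrial fibrillation at the time of enrollment". Section 6.4.1 adds: "Subjects who present with active atrial fibrillation during their regular doctor visit will be recruited for the study". Section 7.3.2 nevertheless has a No AFIB reference column, from which specificity and the false alarm rate are calculated.

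Three passages leave room for other arrangements. Section 6.1 says that validation may use this study's data "in addition to data from other Masimo sponsored studies". Section 7.4 speaks of a sample size per group, although only one group is defined. Section 7.3.2 counts negative events, and 6.4.3.6 has plural measurements ("The subject will be requested to take manual ECG measurements on the INVSENSOR00057"), so the unit of analysis may be the recording.

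**The concern.** An exclusion made after the data are in, and on a feature related to the test result, can change the accuracy estimate. A wrist trace that does not look like AF is a plausible reason for a device output of No AFIB. If that trace counts as evidence for exclusion, or if the reader knows the device result, a subject in AF on the reference whom the device missed can leave the sensitivity denominator.

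Reading the bullet as reference-only removes that problem but exposes another. Every subject enters in AF, so the only reference-negative subjects this cohort can produce are those no longer in AF at recording. The bullet removes exactly those subjects. Both halves of the primary endpoint are therefore affected, one under each reading.

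**Working it through.** **Plan's own figure.** The synopsis gives about 100 subjects. This cannot be reproduced because the inputs in 7.2 are redacted. Section 7.1 gives no numerical acceptance criterion. All counts below are assumed and serve only to show scale.

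**Reading A: the test trace counts, or the reader is unmasked.** From 7.3.2, sensitivity = TP/(TP + FN). Assume 100 reference-AF subjects. Intervals are exact (Clopper-Pearson) 95%.

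| Assumed situation | Sensitivity | 95% CI |
|---|---|---|
| No exclusion, 10 misses | 90/100 = 90.0% | 82.4 to 95.1 |
| 1 miss dropped | 90/99 = 90.9% | 83.4 to 95.8 |
| 3 misses dropped | 90/97 = 92.8% | 85.7 to 97.0 |
| 3 true positives dropped | 87/97 = 89.7% | 81.9 to 94.9 |
| 3 of each dropped | 87/94 = 92.6% | 85.3 to 97.0 |
| No exclusion, 5 misses | 95/100 = 95.0% | 88.7 to 98.4 |
| 3 of those 5 misses dropped | 95/97 = 97.9% | 92.7 to 99.7 |

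The rule acts on a human reading of the waveform, not on the algorithm's output. A miss on a wrist trace that clearly shows AF is kept. A true positive on a trace judged not to be AF is lost. The net direction depends on how strongly trace appearance and output agree. They are likely to agree, so upward bias is probable but not certain.

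**Reading B: the reference alone decides.** Suppose that (i) analysis is by subject and (ii) the reading that triggers exclusion also sets the 7.3.2 label. Every reference-negative subject is then excluded, so FP = TN = 0 and

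- false alarm rate = FP/(FP + TN) = 0/0, and specificity is likewise undefined;
- Accuracy = (TP + TN)/(TP + FP + FN + TN) = TP/(TP + FN), which is sensitivity.

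The readable text settles neither condition. If recordings are the unit, negative recordings may remain from subjects who are not excluded. Section 7.3.2 does not say who assigns the reference label.

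**If reference-negatives are kept.** When all n are true negatives, the exact lower limit is 0.025^(1/n):

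- n = 2: 0.158
- n = 5: 0.478
- n = 10: 0.692
- n = 17: 0.805 (n = 16 gives 0.794)
- n = 36: 0.903 (n = 35 falls just short of 0.90)

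With 8/10 the interval is 0.444 to 0.975. A handful of subjects who have left AF makes specificity calculable but cannot support a performance claim.

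**The case against.** The strongest reply is that the second bullet asks whether a subject who presented in AF still has it, which is a question for the comparator. The first bullet names both tracings when both are meant; the second does not. That is the more natural reading, and a masked read of the reference alone loses no device misses. This stands. It does not help specificity, because under that same reading the bullet takes out the reference-negatives.

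Four stronger inferences are tempting, and the documents do not support them.

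- *The readers are unmasked.* Parts of 6.4.3 and 7.2 are redacted and may describe masking. One can say only that no readable text states it.
- *The exclusion can only flatter the device.* It cannot be said to run one way: losing three true positives gives 87/97 = 89.7%, below the 90.0% start.
- *This bullet is why specificity cannot be estimated.* The main cause is AF-only entry into a single arm (6.1, 6.3, 6.4.1). Rewording the bullet does not cure that.
- *The programme has no specificity data.* Other sponsor studies (6.1), a further group hinted at in 7.4, or redacted text may supply them. No readable text says which.

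It is also fair to say that no document gives a frequency for any of these events, and that each illustrative shift lies inside the interval before exclusion.

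**Conclusion.** The concern holds in a limited form and should be corrected. As written, the second exclusion is open to two readings, and each can harm part of the primary endpoint.

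Under the less natural reading, or with an unmasked reader, sensitivity is probably biased upward. In the examples the change runs from -0.3 points (90.0% to 89.7%) to +2.9 points (95.0% to 97.9%), wholly on assumed counts. Under the more natural reading, specificity from this cohort is 0/0 if analysis is by subject and one reading sets both label and exclusion. If those conditions fail, some negatives may survive, but probably too few to be informative.

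Confidence is medium, because redacted text may settle masking, the unit of analysis or the source of specificity data.

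**What to change.** 1. **Replace the second bullet of 7.3.1** with text such as: *AF status of each paired recording is assigned from the reference ECG alone, by medical personnel masked to the INVSENSOR00057 trace and output. The rhythm appearance of the test trace never excludes a subject or recording. Reference recordings without AF are kept in the No AFIB column and out of the sensitivity denominator.*
2. **State the unit in 7.3.2.** Either score per paired recording, with confidence intervals that allow for several recordings per subject, or score per subject, with a rule for subjects who have both AF and non-AF recordings.
3. **Close the same route through the first bullet.** Judge test readability on signal quality only, masked to the device classification and to the reference rhythm. The same personnel can do this by reading test traces first, or in a separate shuffled order. Report unreadable exclusions by device classification and reference status, and add a sensitivity analysis that counts unreadable test ECGs on reference-AF recordings as misses.
4. **Settle specificity.** Report this cohort's specificity as descriptive with its exact interval (allowing for repeated recordings if they are the unit). In 6.1, 7.2 and 7.3.2, either name the data that supply the main specificity estimate, or restate this study's primary endpoint and sample size basis as sensitivity only.

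The cost is rewording in four sections plus ordered, masked reads; no extra subjects or readers are needed. Sensitivity may come out slightly lower, specificity from this cohort will be imprecise, and the endpoint may have to be narrowed.
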